## **8.5 Sample size calculation**

The sample size has been estimated based on the primary outcome of the study, i.e., the mean change of VA from baseline to 12 months after the initiation of treatment with ranibizumab.

The sample size calculation was conducted with the precision-based sample size calculation.

The 95% CI of the mean change in VA from Baseline to Month 12 was estimated with a precision of about  $\pm 2$  letters (i.e. with a margin of error of 2 letters), that means that we required the 95% CI to be no wider than 4 letters. A search in published data indicated that, based on the results from the phase IV TWIN Study, the estimated standard deviation for the change in VA noted at 12 months of treatment with ranibizumab 0.5 mg in daily clinical practice was 15.4 letters (31). Thus we would have sufficient precision if we enrolled at least 228 patients.

In order to compensate for a potential dropout rate of 10%, a total number of 251 patients should be enrolled in the study.

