#### **5.1.5 Visual acuity**

Effectiveness of ranibizumab treatment will be described by change in VA of the study eye from baseline. Effectiveness cannot be described if VA at baseline is missing. Therefore it is recommended to document VA in the Visual Acuity page of the electronic CRF at the Baseline visit.

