## **8.3 Primary Effectiveness Outcome Analyses Variables**

The analysis of the primary objective of the study will be performed in the per protocol set with available data pertaining to the study primary endpoint, i.e. baseline and 12-month VA data.

The mean change in VA from baseline to month 12 along with the 95% confidence interval (CI) will be calculated for subjects completing 12 months of follow-up. Paired sample t test will be applied to compare the 12-month VA to Baseline VA.

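### Section 8.5 raises 228 to 251 for 10% dropout where 254 is needed, and the allowance names dropout but no other loss from the primary analysis set

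*Protocol*

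**What the plan says.** Protocol section 8.5 plans on precision, not power. The target is introduced loosely ("The 95% CI of the mean change in VA from Baseline to Month 12 was estimated with a precision of about" ±2 letters) and then stated as a limit: "we required the 95% CI to be no wider than 4 letters". The SD of the 12-month change, 15.4 letters, is taken from a published phase IV study in daily practice. From this the section concludes: "Thus we would have sufficient precision if we enrolled at least 228 patients". It then adds: "In order to compensate for a potential dropout rate of 10%, a total number of 251 patients should be enrolled in the study". No other kind of loss is mentioned there.

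The primary analysis is defined in sections 8.1 and 8.3. Section 8.3 says that it "will be performed in the per protocol set with available data pertaining to the study primary endpoint", meaning VA at both baseline and 12 months. Section 8.1 defines the per protocol set as completers with no major deviation. Section 4.4.2 states that withdrawn patients are not replaced.

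On baseline VA, section 5.1.5 notes that effectiveness cannot be described without it and goes on: "Therefore it is recommended to document VA in the Visual Acuity page of the electronic CRF at the Baseline visit". The opening of section 5 says that an X in Table 5-1 marks data that are required. The table has an X for VA at baseline, during observation and at end of study, but its own title calls the schedule recommended.

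**The concern.** There are two separate problems.

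- **The inflation formula.** To end with n patients after a fraction d is lost, enrolment must be n/(1 − d). Multiplying by (1 + d) always falls short. Section 8.5 says that 251 compensates for 10% dropout, and on its own inputs it does not quite do so.
- **What the allowance covers.** The 228 has to be the number in the primary analysis, because the CI is computed on those patients. The allowance is worded for dropout only. A patient who completes the study with a major deviation, or who attends but has no VA recorded at baseline or month 12, is not a dropout and still does not contribute to the primary CI.

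The CI width is the only quantitative design property the protocol states: section 8 says the study tests no pre-defined hypothesis, and section 8.6 gives no power for secondary variables. The sample size section should therefore describe correctly the precision that the planned number will give.

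**Working it through.** **Inputs.** From section 8.5: two-sided 95% CI (z = 1.96), half-width E = 2 letters, SD = 15.4 letters, dropout d = 10%, stated results 228 and 251. From sections 8.1 and 8.3: the primary analysis set. Loss rates above 10% are my assumptions, since the protocol gives none.

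**Step 1: reproduce 228.** n = (z × SD / E)² = (1.96 × 15.4 / 2)² = 15.092² = 227.8, rounded up to 228. This matches. The width at 228 is 2 × 1.96 × 15.4 / √228 = 3.998 letters.

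**Step 2: reproduce 251.** 228 × 1.1 = 250.8, rounded up to 251. This matches. The inflation that keeps 228 is 228 / 0.9 = 253.3, rounded up to 254. The difference is 3 patients (3/254 = 1.2%).

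**Step 3: what 251 gives at the protocol's own 10%.** 251 × 0.9 = 225.9, about 226 patients. Width = 2 × 1.96 × 15.4 / √226 = 4.016 letters, half-width 2.01. The limit of 4 is exceeded by 0.016 letters. With 254 enrolled, 254 × 0.9 = 228.6, and the limit is met.

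**Step 4: the loss that 251 can bear.** 1 − 228/251 = 0.0916, so at most 9.2% in total (23 patients) from all causes.

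**Step 5: larger total loss from the primary set.** Patients analysed are rounded down to whole patients, except 225.9, which is taken as 226.

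| Total loss from 251 | Analysed | Half-width (z) | Full width | Enrolment to keep 228 |
|---|---|---|---|---|
| 10% (section 8.5) | 226 | 2.01 | 4.02 | 254 |
| 15% (assumed) | 213 | 2.07 | 4.14 | 269 |
| 20% (assumed) | 200 | 2.13 | 4.27 | 285 |
| 25% (assumed) | 188 | 2.20 | 4.40 | 304 |
| 30% (assumed) | 175 | 2.28 | 4.56 | 326 |

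**Step 6: which losses lie outside dropout.** Section 4.4 lets a patient be considered withdrawn after fewer than three visits a year, counting the baseline and end-of-study visits, or if lost to follow-up for another reason. Many missed month-12 visits can therefore already fall under dropout. The losses that clearly come on top are completers with a major deviation and attended visits without a recorded VA.

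**The case against.** The strongest reply is that the slip has no practical weight. It costs 3 patients and 0.016 letters against a precision introduced as approximate, and sections 3 and 4 plan for approximately 251 patients. An SD of 15.34 instead of 15.4 would remove the miss. The study is single-arm and observational, no decision depends on a width of exactly 4 letters, and the reported CI will show the precision achieved. All of this stands, and it is why the slip counts as minor. It does not make 251 the right result of the stated calculation, and it does not answer the question of what the 10% covers.

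Three stronger readings are tempting, and the document does not support them.

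- **The t quantile.** Because a paired t test accompanies the CI, a reader might say that 228 is itself too small: with t the width at 228 is 4.02, and 231 would be needed. Section 8.5 does not fix a quantile, the conventional z formula reproduces 228 exactly, and planning with z while analysing with t is ordinary practice. This is a preference and not an error.
- **A large shortfall.** A reader might infer from the table that the study will miss its target by a wide margin. The rows from 15% upwards are illustrations. The only rate in the protocol is 10%, and some missed month-12 visits are already counted as withdrawal.
- **Baseline VA as optional.** Section 5.1.5 read alone suggests that baseline VA may often be missing. Section 5 and the X in Table 5-1 mark it as required, without the asterisk that flags optional items such as the ocular examination. This is an inconsistency in wording and no evidence of expected missing data.

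**Conclusion.** The point holds in a limited form. On the protocol's own inputs, 251 is the wrong inflation of 228 for 10% dropout. The right figure is 254, and 251 leaves an expected width of 4.02 letters against a limit of 4. That miss is minor, and the limit is met if total loss is at most 9.2%.

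The allowance is also described as dropout only, while the primary analysis set loses patients by further routes for which no rate is given. How far this widens the interval cannot be determined from the protocol. If total loss were 15% to 30%, the expected width would be about 4.14 to 4.56 letters. All widths rest on an SD of 15.4 and the normal quantile. The 10% row uses the protocol's rate, and the others use assumed rates.

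Confidence is high for the difference between 251 and 254 and for the mismatch between section 8.5 and sections 8.1 and 8.3. The document does not support saying that the study will materially fail its precision target.

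**What to change.** 1. In section 8.5, either change the total to 254 (and the matching figure in the synopsis and sections 3 and 4), or keep 251 and restate the precision as about ±2.01 letters at 10% loss.
2. Define the allowance as all loss from the primary analysis set: dropout, major deviations, and missing baseline or month-12 VA. State the assumed rate d and apply N/(1 − d).
3. Add one line with the precision at assumed larger losses for 251 enrolled: about ±2.07 letters at 15%, ±2.13 at 20% and ±2.28 at 30%.
4. Bring the wording for baseline VA in section 5.1.5 and the title of Table 5-1 into line with the statement in section 5 that items marked X are required.

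The cost is a text correction and a slightly less favourable stated precision, or 3 more patients if 254 is chosen. If the sponsor assumes a higher total loss and wants to keep 228 analysed, enrolment would have to rise further (for example 269 at 15% or 285 at 20%). Restating the precision avoids that.

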## **8.6 Power for analysis of key secondary variables**

Not applicable.

## **8.7 Interim analyses**

No interim analyses are planned for the study.

# **9 Ethical and regulatory considerations**

## **9.1 Regulatory and ethical compliance**

This study is an observational study where the treatment decision falls within current practice and the prescription of the medicines is clearly separated from the decision to include the patient in the study. No additional diagnostic or monitoring process is required for participation or during the study.

The study was designed and will be conducted in compliance with the protocol and in accordance with the ICH guidelines for GCP, with the ethical principles laid down in the Declaration of Helsinki and with the EOF regulations.

### **CONFIDENTIAL**

This document is confidential and the property of individual. No part of it may be transmitted, reproduced, published, or used by other persons without prior written authorization from the author.

Data protection and privacy regulations will be observed in capturing, forwarding, processing, and storing patient data.

## **9.2 Responsibilities of the investigators and IRB/IEC**

The protocol and the proposed informed consent form must be reviewed and approved by a properly constituted IRB or IEC before study start. A signed and dated statement that the protocol and informed consent have been approved by the IRB/IEC must be given to the Sponsor before study initiation where applicable. Prior to study start, the investigator is required to sign a protocol signature page confirming his/her agreement to conduct the study in accordance with these documents and all of the instructions and procedures found in this protocol and to give access to all relevant data and records to the CRO's monitors, auditors, designated agents of the Sponsor, IRBs or IECs, and regulatory authorities as required. If an inspection of the clinical site is requested by a regulatory authority, the investigator must inform the Sponsor and/or CRO immediately that this request has been made.

Any amendment to the protocol will require review and approval by the IRB/IEC before the changes are implemented in the study.

## **9.3 Informed consent procedures**

Informed consent is a process that is initiated prior to the individual agreeing to participate in the study and continues throughout study participation. Extensive discussion of risks and possible benefits of study participation will be provided to participants and their families, if applicable. A consent form written in Greek language, must comply with the ICH GCP guideline and regulatory requirements and describe in detail the study procedures and risks. The consent form will be provided by the CRO to the study sites after IRB- or IEC-approved and be given to the participant. The participant is required to read and review the document or have the document read to him or her. The investigator or designee will explain the research study to the participant and answer any questions that may arise. The participant will sign the informed consent document prior to any study-related assessments or procedures.

Participants will be given the opportunity to discuss the study with their surrogates or think about it prior to agreeing to participate. They may withdraw consent at any time throughout the course of the study. A copy of the signed informed consent document will be given to participants for their records. The rights and welfare of the participants will be protected by emphasizing to them that the quality of their clinical care will not be adversely affected if they decline to participate in this study.

### **CONFIDENTIAL**

This document is confidential and the property of individual. No part of it may be transmitted, reproduced, published, or used by other persons without prior written authorization from the author.

The process of obtaining informed consent should be documented in the patient source documents.

## **9.4 Participant Confidentiality**

Participant confidentiality is strictly held in trust by the investigators, study staff and the Sponsor and its agents. This confidentiality is extended to cover testing of biological samples and genetic tests in addition to any study information relating to participants.

The study protocol, documentation, data, and all other information generated will be held in strict confidence. No information concerning the study or the data will be released to any unauthorized third party without prior written approval of the Sponsor.

The CRO's monitors, auditors, designated agents of the Sponsor, IRBs or IECs, and regulatory authorities may inspect all study documents and patient records and source documents required to be maintained by the investigator. The clinical study site will permit access to such records.

## 10 Data handling and record keeping

The investigators are responsible for ensuring the accuracy, completeness, legibility, and timeliness of the data reported. All source documents should be completed in a neat, legible manner to ensure accurate interpretation of data. The investigators will maintain adequate case histories of study participants and source documentation.

### 10.1 Storage of source documents and archiving

Study staff will maintain appropriate medical and research records for this study, in compliance with ICH GCP guidelines and with topical regulatory and institutional requirements for the protection of confidentiality of subjects. Study staff will permit authorized representatives of CRO and regulatory agencies to examine (and when required by applicable law, to copy) research records for the purposes of quality assurance reviews, audits, and evaluation of the study safety, progress and data validity.

After DBL, the investigator will receive a CD-ROM or paper copies of the patient data entered in the electronic CRFs for archiving at the study site.

The PI will make sure that all relevant documents and source documents of this observational study will be stored at a secure and locked place in the site after end or discontinuation of the study according to the local regulation.

## 11 Protocol adherence

This observational study protocol does not direct therapy or dictate any treatment other than that patients be treated in accordance with the ranibizumab approved local SPC.

### 11.1 Protocol Amendments

Any change or addition to the protocol can only be made in a written protocol amendment that must be approved by the Sponsor, Health Authorities and the IRB or IEC, where required. Only amendments that are required for patient safety may be implemented prior to IRB or IEC approval. Notwithstanding the need for approval of formal protocol amendments, the investigator is expected to take any immediate action required for the safety of any patient included in this study, even if this action represents a

#### **CONFIDENTIAL**

This document is confidential and the property of individual. No part of it may be transmitted, reproduced, published, or used by other persons without prior written authorization from the author.

deviation from the protocol. In such cases, the Sponsor and the CRO should be notified of this action and the IRB or IEC at the study site should be informed within 10 working days.

## **11.2 Protocol Deviations**

A protocol deviation is any noncompliance with the clinical study protocol. The noncompliance may be on the part of the subject, the investigator or study staff. Investigators ascertain they will apply due diligence to avoid protocol deviations. As a result of deviations, corrective actions are to be developed by the study staff and implemented promptly. All significant protocol deviations will be recorded and reported in the clinical study report.

## **12 Publication of results**

Sponsor assures that the key design elements of this protocol will be posted in a publicly accessible database. In addition, upon study completion and finalization of the study report the results of this trial will be either submitted for publication and/or posted in a publicly accessible database of clinical trial results. No individual investigator may publish on the results of this study without prior approval from the sponsor.

